Neuromyelitis optica spectrum disorder (NMOSD) is a chronic relapsing autoimmune disease of the central nervous system (CNS) that preferentially targets the optic nerves and spinal cord, leading to paralysis, blindness and death. NMOSD is a rare disease that affects approximately 4,000-8,000 (1-2:100,000 persons in the US) people in the United States, disproportionately affects non-Caucasians and females, and has a worldwide prevalence estimated to be 0.52 to 4.4/100,000. Pain is a severely disabling component of the disease with up to 91% of patients reporting central neuropathic pain (CNP) characterized by agonizing burning, shooting or tingling sensation in the face, arms, torso and legs. NMOSD lesions in the spinal cord are characteristically long and destructive, and pain is more prevalent in NMOSD than in most other neurological diseases. Research on the impact of persistent pain on quality of life (QoL) in NMOSD has found that those patients with CNP experience more depression, less enjoyment of life, and more difficulty with ambulation. Currently, there is no standard of care for CNP treatment and off-label use of medications typically used for diabetic peripheral neuropathy are often insufficient. NMOSD is a devastating disease and there remains a high unmet need for effective treatment of CNP.

Transcutaneous electrical nerve stimulation (TENS) therapy is a non-invasive pain modifying intervention that utilizes transcutaneous electrical stimulation of ascending (sensory) fibers with the intent of re-organizing maladaptive signaling pathways. This neuromodulatory therapy has been investigated for treatment of persistent peripheral neuropathic pain in several conditions including chemotherapy-induced neuropathy, post-herpetic neuralgia and post-surgical neuropathic pain with promising results. Patients report sustained relief after undergoing daily treatment sessions for 10 consecutive weekdays.

Recently we completed a sham-controlled trial using a TENS unit called Scrambler in NMOSD patients showing a meaningful reduction in neuropathic pain compared to controls. The Scrambler device must be operated in an office by a professional technician, thereby limiting its usefulness to the wider NMOSD population. The Quell transcutaneous electrical nerve stimulation device delivers varying electric pulses non-invasively to reduce pain. It is a small, wearable device that utilizes regularly-changing electric pulses to stimulate nerves such that the experience of pain is blocked. Because the Quell Flex is programmable remotely, a sham-controlled trial can be conducted while keeping the patient blinded to the trial arm.

For patients with NMOSD and other conditions that cause pain originating in the central nervous system, non-obtrusive, non-pharmacological devices might prove a viable alternative to pain medications. Pharmaceutical treatments for pain such as opioids have led to addiction and life-style changes with unacceptable side effects. Cost and side effects are concerns with other pharmacologic therapies for pain. In addition, in efforts to control pain, many patients are prescribed multiple medications, and then have to cope with the complexities and hazards of polypharmacy. Most importantly, none of the pharmaceutical treatments for pain in NMOSD have been proven effective in a trial.

TENS for Neuropathic Pain in NMOSD

Principal Investigator: [name], PhD

If we could show among a significant patient cohort that a safe and effective at-home nonpharmacological pain therapy is available for patients with NMOSD, it would be life altering for a great many – not only those with NMOSD, but also with related neuroimmune disorders and other conditions with central neuropathic pain.

The goal of this project is to provide an effective, non-invasive treatment for neuropathic pain in NMOSD that can be safely employed at home. Many NMOSD patients have such chronic pain and/or disability that frequent visits to the clinic for therapy is difficult, if not impossible, in the best of times. Secondly, safe at-home treatments that offer continuous relief of pain (and potentially other co-occurring symptoms) can improve quality of life immensely during this, and likely future times of social distancing, when leaving home is dangerous, especially for a population on lifelong immune suppressants. Also, an at-home therapeutic option will save both time and money for patients.

TENS for Neuropathic Pain in NMOSD

Principal Investigator: [name], PhD

2. Trial Scheme and Objectives

[figure not shown]
2.1. Scheme

Patients will be randomized 1:1 to receive treatment daily for 4 consecutive weeks versus sham, followed by an open-label phase for additional 4 consecutive weeks.

2.2. Primary Objective

The primary objective is to determine the difference in the Numerical Pain Scale score between the baseline screening call and at week 4 in the treatment group compared with the same difference in the placebo or sham group.

The Numerical Pain Scale is an 11-point scale (0-10) that includes guides to assist in the

determination of the pain level.

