3.1. Primary

- QUELL FLEX therapy reduces pain scores in NMO patients on the Numerical Pain Scale at the week 4 study visit compared to baseline/screening visit, and this reduction is significantly greater compared to the reduction due to sham treatment during the same time period. Power for this study is calculated based on our previous study using a TENS unit (Scrambler) in the same patient population.

[figure not shown]

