5.1. Inclusion Criteria

- 5.1.1. Men and women 18 years of age or older diagnosed with NMOSD per the 2015 NMOSD criteria
- 5.1.2. Patients must be positive for the aquaporin-4 antibody in serum
- 5.1.3. Presence of persistent neuropathic pain (≥ 3 months) rated at a level of 4 or higher on the Numerical Pain Scale
- 5.1.4. Patients must be stable in their disease, such that they have had no spinal cord relapses within 6 months prior to enrollment
- 5.1.5. Patients must be on a stable medication regimen that may include anti-epileptic, antidepressant, or non-steroidal anti-inflammatory medications, with no adjustments to the regimen within 30 days of enrollment
- 5.1.6. Pain must be localized to a spinal cord lesion
- 5.1.7. Patient understands the study regimen, its requirements, risks, and discomforts, and is able and willing to sign an informed consent form
- 5.1.8. Patients must own and be able to operate an iOS or Android smartphone with internet connection

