6.5.1.1. Treatment Days

1. Prior to initiation of Quell therapy, patients will be asked to rate their pain on the Numerical Pain Scale and will complete a Short Form-36 Health Inventory (SF-36).
2. All training on the use of the device will be conducted remotely through Zoom.

TENS for Neuropathic Pain in NMOSD

Principal Investigator: [name], PhD

3. Patients will be shipped a QUELL FLEX device. It will either be a functional QUELL FLEX device for the treatment arm or a non-functional QUELL FLEX device in the sham arm. All of the lights, charging equipment, and app connectivity will be the same. The only difference is that the non-functional sham devices will administer an electrical current for only 2 minutes each at the top of a treatment hour, at 30 minutes and at 58 minutes, as opposed to for the full hour when the device is engaged.
4. Patients will be informed that we are conducting a number of different treatment paradigms – some of them have high frequency waves that are not perceptible, and some have lower frequency waves that may be transiently perceptible. In addition, we will re-inform them there is a sham arm.
5. The electrodes will be placed on patients on the back in the dermatome of the most painful area. The intensity of the stimulus is increased until the patient can first feel some sensation associated with the electrodes. Script: “Tell me when you feel something.”
6. Stimulation intensity will be increased until a maximum threshold is tolerated without being painful.
7. Once the intensity is at its maximum setting, the study coordinator will evaluate the level of pain. If the patient feels a constant burn, single sting or feeling of discomfort, the electrodes will be repositioned. The exact electrode positioning will depend on the delimitation of the surface pain area, and analgesic response of the patient.
8. Once satisfactory electrode placement and stimulus intensity is determined, therapy is maintained for at least an hour per day for 4 weeks (both treatment and sham groups).
9. Patients will report pain scores weekly throughout experimental period while on a zoom call with the trial researcher. Patients will again complete all measurement tools and pain ranking at end of treatment.

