6.8.2. Withdrawal from Study

The reasons for withdrawal from the study include:

- Subject withdraws consent for follow-up.
- Subject is lost to follow-up.
- Study is terminated for any reason.

TENS for Neuropathic Pain in NMOSD

Principal Investigator: [name], PhD

7. Table 3: Patient Event Calendar

Phase	Baseline Screening/Consent	Experimental (Weeks)				Open Label (Weeks)				Follow-up (weeks)	
Time Point (days)	Within 2 weeks	1	2	3	4	5	6	7	8	12	16
Exam/Tests *	Consent, MRI review, Q [#]	AE and weekly pain score assessment, Q				AE and weekly pain score assessment, Q				AE and pain score assessment	AE and pain score assessment

#Q: Questionnaire (SF-36)

TENS for Neuropathic Pain in NMOSD

Principal Investigator: [name], PhD

8. Adverse Events

In over 4000 patients treated and reported to the FDA for approval, published and in-press studies, no significant adverse events have been reported with Scrambler and related TENS units.

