11.2. Efficacy

Change in pain score will be calculated by subtracting the patient's week 4 score from his or her baseline value prior to treatment initiation. Change in scores will be summarized using means and standard deviations provided the resulting distribution is symmetric, otherwise medians and interquartile ranges will be used. Provided the resulting distribution of pain scores is roughly normal, we will use a two-sample t-test to compare the QUELL FLEX and sham groups. Previous studies suggest that the average pain value at baseline is at least 4 on the 0-10 numerical rating scale with a standard deviation of the original pain value expected to fall in the range of 1-1.5 in this patient population. As such, a conservative estimate of the standard deviation would be approximately 20%. With 19 patients in each arm and under these assumptions, we will have the ability to detect a change of 2.0 points in the QUELL FLEX group with power of 0.90. If the change score distribution is highly skewed, Wilcoxon's signed rank test will be utilized instead.

To account for ~20% dropout rate, we will add 4 subjects to each arm for a total of 23 subjects per arm. We included a dropout rate of ~20% based on previous studies with this device. We will run a sensitivity analysis to determine if the drop-out rate in either arm had an impact on the trial results.

A 20% reduction in pain has been previously determined to be a clinically meaningful improvement, we will report the number and percent of patients from each group who achieve this benchmark.

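### The plan does not say that the baseline pain score is separate from the score that qualified the patient, so changes measured without a control group and each arm's 20% responder rate may include regression to the mean

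*Combined protocol and SAP*

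**What the plan says.** - **Section 2.2** takes the primary change "between the baseline screening call and at week 4" under active treatment and compares it with the same change under sham. Objectives 2.3 B and C use the screening call for their week-4 comparison of worst and average pain. Their week-8 clause, for all subjects together, says only baseline.
- **Section 3.1** merges the two occasions: "at the week 4 study visit compared to baseline/screening visit".
- **Section 11.2** computes change by "subtracting the patient's week 4 score from his or her baseline value prior to treatment initiation". It does not say at which contact that value is obtained.
- **Section 6.5.1.1, step 1** plans a rating: "Prior to initiation of Quell therapy, patients will be asked to rate their pain on the Numerical Pain Scale". It is not tied to the screening call or to any later contact, and it stands before the steps on training and shipping.
- **Section 6.6.1** has the scale given at every study visit.
- **Section 7, Table 3** has one pre-treatment column, covering screening and consent within 2 weeks. Its content is "Consent, MRI review, Q", with Q defined as the SF-36. Pain scores first appear under weeks 1 to 4.
- **Section 5.1.3** admits patients with persistent pain "rated at a level of 4 or higher on the Numerical Pain Scale".

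Nothing states whether the qualifying score and the analysis baseline are one measurement or two.

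**The concern.** The primary endpoint is a change score, so its starting point should be one identified measurement. Here it could be the screening-call score or a later pre-treatment rating. If both exist, the plan leaves the choice open until data are in hand.

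The screening score has a further problem. Patients enter because that score is 4 or higher, so on average it sits above their usual level, and later ratings fall back even if the device does nothing. A change measured from it counts that fall as improvement. Two kinds of result are exposed:

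- the week-8 changes in 2.3 B and C, which have no control group;
- the percentage in each arm reaching the 20% benchmark of section 11.2. For a patient starting at 4 that is only 0.8 points. A similar 20% split feeds the quality-of-life analysis in 11.3.

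**Working it through.** The plan gives no figure on this point to reproduce. The check sizes the regression to the mean.

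**Inputs.** The cut is 4 (5.1.3). The SD is 1 to 1.5 (11.2). The mean μ of the screened population (4 to 6) and the reliability r (0.5 to 0.8) are assumptions: 11.2 says only that the average baseline is at least 4. Ratings are taken as normal and equally correlated.

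**1. Spurious fall when the qualifying score is the baseline.** With a = (4 − μ)/SD and λ = φ(a)/(1 − Φ(a)), selection raises the mean score by SD × λ, and a later rating loses (1 − r) of that.

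- μ = 5, SD 1.5: a = −0.667, λ = 0.3194/0.7475 = 0.427, excess 0.641. Fall = 0.5 × 0.641 = 0.32 at r = 0.5, and 0.2 × 0.641 = 0.13 at r = 0.8.
- Largest case, μ = 4, SD 1.5, r = 0.5: λ = 0.798, fall = 0.5 × 1.5 × 0.798 = 0.60.
- Smallest case, μ = 6, SD 1, r = 0.8: λ = 0.055, fall = 0.2 × 0.055 = 0.01.

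With a separate baseline the expected fall is 0, because that rating and the later one have both regressed.

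**2. Whole-number ratings.** On an 11-point scale, 4 or higher corresponds roughly to a latent cut at 3.5. For μ = 5, SD 1.5: a = −1, λ = 0.2420/0.8413 = 0.288, excess 0.431. The fall is 0.22 (r = 0.5) to 0.09 (r = 0.8), instead of 0.32 to 0.13.

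**3. Share reaching a 20% reduction with no treatment effect** (simulation, continuous scores):

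| Mean, SD, reliability | Qualifying score as baseline | Separate baseline |
|---|---|---|
| 4, 1.5, 0.5 | 37% | 25% |
| 5, 1.5, 0.6 | 24% | 19% |
| 5, 1.5, 0.8 | 13% | 11% |
| 6, 1.5, 0.6 | 18% | 16% |

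**4. Randomised contrast.** In the same simulations the difference between arms in mean change was within 0.01 of 0 under either baseline.

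**5. Averaging two pre-treatment ratings as a covariate.** Relative to the week-4 variance, the adjusted variance is 1 − r² with one rating and 1 − 2r²/(1 + r) with the mean of two. The ratio is (1 + 2r)/(1 + r)². At r = 0.5 it is 2/2.25 = 0.889, an 11% reduction. At r = 0.8 it is 2.6/3.24 = 0.802, a 20% reduction.

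**The case against.** The strongest reply is that the sections do not conflict. A screening-call score is also a value obtained before treatment, 3.1 treats baseline and screening as one visit, and Table 3 has a single pre-treatment column. Step 1 pairs the pain rating with the SF-36, whose only pre-treatment entry is in that column, so step 1 may simply be the screening contact. This stands: a reader might infer two contradictory baseline definitions, and the documents show an ambiguity instead. But this reading makes one score serve for both selection and baseline, which is the exposure described here.

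A reader might also infer from Table 3 that no baseline pain score is collected. Sections 6.5.1.1 and 6.6.1 show that one is planned, so the calendar entry is incomplete.

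The affected results are also limited. Objective 2.3 A compares week 8 with week 4 and uses no baseline. The responder counts have a concurrent sham arm, so their comparison between arms is protected in a way that the absolute percentages are not. Section 5.1.3 does not say which rating qualifies a patient, so the computed fall may not carry over fully to the worst and average scores.

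Finally, the mean and reliability are assumed, and the SD in 11.2 is not shown to describe an unselected screening pool. That is why a range is given. At mean 6 and SD 1 the effect is negligible.

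**Conclusion.** The concern holds as an ambiguity that should be closed. Read literally, the plan lets the qualifying score be the baseline. In that case the single-group week-8 changes in 2.3 B and C and the absolute 20% responder percentages are inflated. The spurious fall is about 0.01 to 0.6 points over means 4 to 6, SD 1 to 1.5 and reliability 0.5 to 0.8, with a continuous cut. For mean 5 and SD 1.5 it is 0.13 to 0.32, or about 0.09 to 0.22 with whole-number ratings.

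The stronger inference, that the primary result is biased, is not supported: selection precedes treatment and acts on both arms equally.

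**What to change.** In 2.2, 2.3 B and C, 3.1, step 1 of 6.5.1.1, 11.2 and Table 3, name one baseline rating and its contact. It should be separate from the qualifying score and taken before the first stimulation, for example at the start of the Zoom training call already planned. State that the screening score serves for eligibility only. For 2.3 B and C, record worst and average pain at the same contact.

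Preferably also adjust the week-4 comparison for pre-treatment pain. If both ratings are kept and equally correlated, using their mean as the covariate instead of one rating cuts the adjusted variance by about 11% to 20%. A reader might expect 25%, but that applies to an unadjusted change score: 2(1 − r) with one rating against 1 + (1 + r)/2 − 2r = 1.5(1 − r) with two.

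**Cost.**
- One extra verbal question and one calendar entry. Step 1 comes before training and shipping, so it cannot be assumed to supply this rating already.
- The rating may fall after randomisation, because the shipped device is arm-specific, but the patient is still blinded.
- Some patients will have a baseline below 4: roughly 11% to 17% at mean 5, SD 1.5 and reliability 0.8 to 0.5. Their eligibility is unaffected.
- Under equal correlation the unadjusted change score becomes slightly more variable, because the qualifying score is truncated (SD 1.28 to 1.34 at mean 5, SD 1.5, reliability 0.6). Adjustment for pre-treatment pain helps to offset this.
- The sample size does not change.

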2.3. Secondary

Six secondary objectives are intended to collect additional information about the potential benefit of QUELL FLEX:

- A. The difference in pain scores at the end of the open label phase compared to the end of the initial blinded phase.
- B. A change in the “worst” pain score in the treatment arm vs. the sham arm between the baseline screening call and week 4; and the change in the “worst” pain from baseline to week 8 for all subjects.
- C. A change in the “average” pain score in the treatment arm vs. the sham arm between the baseline screening call and week 4; and the change in the “average” pain from baseline to week 8 for all subjects.
- D. The number of patients who withdraw because of poor compliance. We expect a higher withdrawal and non-compliance rate in the sham group.
- E. Quality of life surveys will be conducted before and after the treatment phase and at the end of the study to determine if the QUELL FLEX treatment impacts overall quality of life.
- F. Reduction in pain medication use over the course of the study.

TENS for Neuropathic Pain in NMOSD

Principal Investigator: [name], PhD

3. Hypotheses

3.1. Primary

- QUELL FLEX therapy reduces pain scores in NMO patients on the Numerical Pain Scale at the week 4 study visit compared to baseline/screening visit, and this reduction is significantly greater compared to the reduction due to sham treatment during the same time period. Power for this study is calculated based on our previous study using a TENS unit (Scrambler) in the same patient population.

[figure not shown]
3.2. Secondary

- QUELL FLEX therapy is an acceptable treatment measured by compliance and patient survey.
- Patients who were randomized initially to the sham arm will show a reduction in pain score after crossing over into the open label arm. In contrast, the patients in the treatment arm will not necessarily show additional benefit after rolling over in the open label arm.
- The “average” and “worst” pain scores will decline in the treatment arm and not necessarily in the sham arm.
- As pain is a primary driver of quality of life, quality of life will improve with treatment compared to sham.
- Patients for whom QUELL FLEX works well may choose to reduce their intake of pain medications.

4. Background and Rationale

4.1. Etiology and current treatment of central neuropathic pain in patients with neuromyelitis optica spectrum disorder

Neuromyelitis optica spectrum disorder (NMOSD) is an autoimmune disease of the central nervous system (CNS) that preferentially causes recurrent inflammatory attacks in the optic nerves and spinal cord, leading to blindness, paralysis and death. Despite these devastating consequences of the disease, patients have reported that pain is among the most prevalent and debilitating symptoms.

In particular, central neuropathic pain (CNP) is pervasive, severe, intractable to treatment, and affects 62-91% of patients with NMOSD. CNP is described as agonizing burning, stabbing, shooting, tingling or squeezing

Figure 1. Cross-section of the spinal cord depicting spinal tracts.

From:

sensation that is distressing, persistent and incapacitating. While the severity of CNP in NMOSD is not well-understood, its presence is a direct consequence of targeted immune-mediated destruction of the spinal cord and occurs at and below the spinal cord lesion level, and may be a result of damage to ascending sensory pathways where there is inadequate stimulation of peripheral sensory nerve endings. Ascending (sensory) pathways are nerves that go upward from the spinal cord toward the brain carrying sensory information from the body to the brain. In contrast, descending (motor) pathways are nerve pathways that go down the spinal cord and allow the brain to control movement of the body below the head (Figure 1). As a consequence of ongoing spontaneous activity arising in the periphery, surviving neurons develop increased background activity, enlarged receptive fields and increased responses to ascending nerve impulses, including normally harmless tactile stimulation.

TENS for Neuropathic Pain in NMOSD

Principal Investigator: [name], PhD

4.2. TENS Therapy: potential application to central neuropathic pain

4.2.1. Rationale for nerve-based treatments

Scrambler Therapy is a new, non-invasive technology with Food and Drug Administration (FDA) 510(k) approval, "Scrambler ST 5 TENS Device," (K081255) granted in February 2009. It uses cutaneous electrostimulation that simulates normal nerve action potentials. The impulses are transmitted via surface electrodes placed surrounding the pain area along the same nerve pathways, done by following the dermatomes and avoiding areas that hurt (Figure 2). The device synthesizes 16 different types of nerve action potentials similar to the endogenous kinds, strings them into sequences, and directly stimulates the nerves. These different waveforms are dynamically assembled into strings of information that are recognized by the CNS and replace pain with "no-pain" information. Neuroplasticity enables these new signals to replace the old, inappropriate amplification of pain signals. Scrambler therapy provides 16 continuously changing variable nonlinear waveforms, or a "scrambled" signal, thus making it different from transcutaneous electrical nerve stimulation (TENS), which provides an on-off, biphasic waveform. TENS is thought to block the pain signal rather than replace it with new information, which translates into often short-lived results that are not as practical for persistent pain. Data in Scrambler therapy, on the other hand, suggests that patients can have significantly reduced pain or be pain-free for up to 3 months following a series of treatments, and that follow-up treatments may require fewer sessions for continued relief, including limited data from randomized controlled trials. The exact mechanism by which Scrambler Therapy relieves pain is under investigation.

Figure 2. A picture of the machine with electrode placement. Permission from [name]

OH DEAR. THE ENDNOTES ARE ALL MESSED UP.

